12.7 Interim analyses

No interim analysis is planned for this trial. A final analysis will be performed after all subjects have completed Week 12 or discontinued prior to Week 12.

12.8 Sample size calculation

12.8.1 Primary endpoint(s)

Assuming a true treatment difference in change from baseline in weekly mean pain severity VAS of 15 mm and a SD of 23 mm, a sample size of 50 subjects per arm provides approximately 83% power that the primary analysis will be statistically significant at the two-sided 5% significance level adjusted by 2 comparisons.

See Table 12-1 for power to detect a significant difference from placebo under various assumed treatment effect of weekly mean pain severity VAS and SD.

nQuery Advisor 7.0 is used for the estimate.

Table 12-1 Power to detect a significant difference from placebo under different assumed treatment effects and SD with N = 50 pts/arm

	Treatment effect: difference from placebo in change from baseline in weekly mean pain severity VAS			
SD of change from baseline in weekly mean I pain severity VAS	15	20		
17	98%	>99%		
20	92%	>99%		
23	83%	97%		

The sample size may increase by up to 20% (i.e., 60 pts/arm) in order to maintain power in case dropout increases during the pandemic.

13 Ethical considerations and administrative procedures

13.1 Regulatory and ethical compliance

This clinical study was designed and shall be implemented, executed and reported in accordance with the ICH Harmonized Tripartite Guidelines for GCP, with applicable local regulations (including European Directive 2001/20/EC, US CFR 21), and with the ethical principles laid down in the Declaration of Helsinki.

13.2 Responsibilities of the investigator and IRB/IEC

Before initiating a trial, the investigator/institution must obtain approval/favorable opinion from the Institutional Review Board/Independent Ethics Committee (IRB/IEC) for the trial protocol, written informed consent form, consent form updates, subject recruitment procedures (e.g. advertisements) and any other written information to be provided to subjects. Prior to study start, the investigator is required to sign a protocol signature page confirming his/her agreement to conduct the study in accordance with these documents and all of the instructions and procedures found in this protocol and to give access to all relevant data and records to Novartis study monitors, auditors, Novartis Quality Assurance representatives, designated agents of Novartis, IRBs/IECs, and regulatory authorities as required. If an inspection of the clinical site

is requested by a regulatory authority, the investigator must inform Novartis immediately that this request has been made.

13.3 Publication of study protocol and results

The protocol will be registered in a publicly accessible database such as clinicaltrials.gov and as required in EudraCT. In addition, after study completion (defined as last patient last visit) and finalization of the study report the results of this trial will be submitted for publication and posted in a publicly accessible database of clinical trial results, such as the Novartis clinical trial results website and all required Health Authority websites (e.g. Clinicaltrials.gov, EudraCT etc.).

For details on the Novartis publication policy including authorship criteria, please refer to the Novartis publication policy training materials that were provided to you at the trial investigator meetings.

13.4 Quality Control and Quality Assurance

Novartis maintains a robust Quality Management System (QMS) that includes all activities involved in quality assurance and quality control, to ensure compliance with written Standard Operating Procedures as well as applicable global/local GCP regulations and ICH Guidelines.

Audits of investigator sites, vendors, and Novartis systems are performed by auditors, independent from those involved in conducting, monitoring or performing quality control of the clinical trial. The clinical audit process uses a knowledge/risk based approach.

Audits are conducted to assess GCP compliance with global and local regulatory requirements, protocols and internal SOPs, and are performed according to written Novartis processes

14 Protocol adherence

This protocol defines the study objectives, the study procedures and the data to be collected on study subjects. Additional assessments required to ensure safety of subjects should be administered as deemed necessary on a case by case basis. Under no circumstances including incidental collection is an investigator allowed to collect additional data or conduct any additional procedures for any purpose involving any investigational drugs under the protocol, other than the purpose of the study. If despite this interdiction prohibition, data, information, observation would be incidentally collected, the investigator shall immediately disclose it to Novartis and not use it for any purpose other than the study, except for the appropriate monitoring on study subjects.

Investigators ascertain they will apply due diligence to avoid protocol deviations. If an investigator feels a protocol deviation would improve the conduct of the study this must be considered a protocol amendment, and unless such an amendment is agreed upon by Novartis and approved by the IRB/IEC and Health Authorities, where required, it cannot be implemented.

MAR	Missing at Random
MedDRA	Medical Dictionary for Drug Regulatory Affairs
mg	milligram(s)
mL	milliliter(s)
ml	milliliter(s)
MMRM	Mixed Model Repeated Measure
NGF	Nerve Growth Factor
OPAS	Ocular Pain Assessment Scale
PK	Pharmacokinetics
PRK	Photorefractive Keratectomy
PRO	Patient-reported Outcomes
REML	Residual/Restricted Maximum Likelihood
RK	Radial Keratotomy
QoL	Quality of Life
SAE	Serious Adverse Event
SAF	Safety Analysis Set
SAP	Statistical Analysis Plan
SD	Standard Deviation
SMILE	Small Incision Lenticule Extraction
SMQ	Standardized MedDRA Query
SOC	System Organ Class
TRPV1	Transient Receptor Potential Vanilloid 1
VA	Visual Acuity
VAS	Visual Analogue Scale
WHO	World Health Organization

Novartis	For business use only	Page 7 of 33
SAP		CSAF312B12201

1 Introduction

The purpose of the Statistical Analysis Plan (SAP) is to describe the implementation of statistical analysis planned in the study protocol, and to provide detailed statistical methods that will be used for the Clinical Study Report (CSR) of study CSAF312B12201.

Data will be analyzed according to the data analysis plan described in this document that will be incorporated into the [CSAF312B12201 CSR-Section 9.7] and [CSAF312B12201 CSR-Appendix 16.1.9].

1.1 Study design

Figure 1-1 Study Design

This study is a Phase 2 randomized, double-blinded, multi-center, parallel group, placebocontrolled evaluation of the safety and efficacy of SAF312, 5 mg/ml and 15 mg/ml eye drops versus placebo used twice-daily in both eyes for 12 weeks. Eligible subjects will have undergone refractive surgery (i.e., PRK, LASIK, LASEK, RK, or SMILE) or cataract surgery in both eyes, with or without refractive enhancement in one or both eyes at least 4 months prior to Screening, and have been suffering from chronic ocular pain as a result of the surgery. Both eyes do not necessarily need to have undergone surgery on the same day. If the second eye underwent surgery on a different day than the first eligibility for time since surgery would be based on the date of the second surgery. In cases where more than one procedure was performed on an eye (e.g. refractive surgery with CICP followed some time later by cataract surgery, or cataract surgery followed some time later by refractive enhancement), the Screening visit must be ≥ 4 months after the most recent procedure. Eligible patients must also demonstrate chronicity of the pain as described in the inclusion criteria.

The study will consist of a 12-week observation period starting from Screening Visit (Visit 1) until the Baseline/Randomization Visit (Visit 2). Subjects who qualify for randomization will then be asked to attend visits every 2 weeks for the first 4 weeks, and then monthly for the

Novartis	For business use only	Page 8 of 33
SAP		CSAF312B12201

remainder of the 12-Week treatment period. End of Treatment (EOT) will occur at Visit 6 when the subject receives the last study treatment. End of Study (EOS) will occur 4 days after EOT. Visit 6/EOT is the time point for primary analysis.

Potential participants will be required to provide written informed consent prior to any studyspecific Screening procedures being performed. Once informed consent is obtained subjects will be evaluated for eligibility based on the inclusion and exclusion criteria. Final eligibility will be based on an assessment of the subject's pain severity VAS prior to randomization, as well as their response to a single drop of topical ocular anesthetic (e.g. tetracaine, proparacaine eye drops per clinical practice). Response to anesthetic is defined as $a \ge 60\%$ reduction in ocular pain within 5 minutes after instillation of the anesthetic drop. The use of the anesthetic test is necessary for the selection of subjects with a primarily peripheral neuropathic type pain (i.e. primarily resulting from stimulation of the peripheral neuropathic pain are unlikely to experience significant improvement with a topical ocular treatment targeting the peripheral nerves.

Overall, approximately 150 subjects will be enrolled in the study. Subjects who meet eligibility criteria at Visit 2 will be randomized to one of the 3 treatment groups (SAF312 5 mg/mL, SAF312 15 mg/mL, or placebo) in a 1:1:1 ratio. Randomization will be stratified according to baseline mean pain severity over the 7 days prior to Baseline Visit (\geq 75 mm or <75mm).

No interim analysis planned.

1.2 Study objectives and endpoints

Objective(s)		Endpoint(s)		
Primary objective(s)		En	dpoint(s) for primary objective(s)	
•	To demonstrate the efficacy of at least 1 of 2 concentrations of SAF312 (5 mg/ml or 15 mg/ml) with superiority to placebo in reducing ocular pain severity	•	Change from baseline to Week 12 in weekly mean pain severity Visual Analog Scale (VAS)	
Se	condary objective(s)	En	dpoint(s) for secondary objective(s)	
•	To evaluate additional efficacy of 2 concentrations of SAF312 vs placebo	•	Change from baseline to Day 7 and Day 14 using the pain severity VAS	
		•	Change from baseline to Week 12 in pain frequency VAS	
		•	Change from Baseline to Week 12 in Ocular Pain Assessment Scale (OPAS) sub-scale Quality of Life	
•	To demonstrate SAF312 does not induce negative effects to the ocular surface after prolonged TRPV1 inhibition	•	Change from baseline to Week 12 in ocular surface parameters (e.g. corneal and conjunctival staining score, Schirmer score, conjunctival redness score)	

Table 1-1Objectives and related endpoints

Novartis SAP	For busine	For business use only		Page 9 of 33 CSAF312B12201	
Objective(s)		En	dpoint(s)		
• To evaluate the safety of SAF312 (0.5 and 1.5%)	of 2 concentrations of	٠	Comparison of adverse ev between active and place	vents rates	
Exploratory objective(s)		En	dpoint(s) for exploratory	objective(s)	
 To monitor a subject's ta artificial tear/gel/lubrication 	ehavior regarding nt use	•	Frequency of artificial tear over the 12-week treatme	/gel/lubricant use nt period	
• To monitor a subject's to rescue medication use	ehavior regarding	•	Frequency of rescue med the 12-week treatment pe	ication use over riod	
 To evaluate corneal ner morphology 	ve density and	•	Change from Baseline to corneal nerve fiber length Presence of microneurom	Week-12 in total as	

2 Statistical methods

2.1 Data analysis general information

The analysis will be performed by the Biostatistics and statistical programming groups of Novartis, using SAS 9.4 or above.

.

Density of corneal dendritiform cells

For categorical variables, frequencies and percentages will be computed. For continuous variables, descriptive statistics, including number of non-missing observations, mean, standard deviation, median, minimum, and maximum will be presented. For selected parameters, 25th and 75th percentiles will also be presented. Where appropriate, point estimates and two-sided 95% confidence intervals of treatment group differences will be provided.

These summary statistics will be presented by treatment group unless otherwise specified.

2.1.1 General definitions

2.1.1.1 Study Treatment

Any drug administered to the study participants as part of the required study procedures; includes investigational drug (s), and control(s), which includes:

Novartis	For business use only	Page 10 of 33
SAP		CSAF312B12201

- SAF312 15 mg/mL (1.5%) eye drops, suspension, b.i.d.
- SAF312 5 mg/mL (0.5%) eye drops, suspension, b.i.d.
- SAF312 Placebo eye drops, suspension, b.i.d.

All dosage strengths of SAF312 and placebo will be identical in appearance (in Drop-tainers for b.i.d. dosing of both eyes each day). The following abbreviated treatment groups will be used as the headers in the tables:

- SAF312 15 mg/ml
- SAF312 5 mg/ml
- SAF312 Placebo

2.1.1.2 Baseline and post-Baseline

Baseline (Day 1) is the date of first dose of study treatment. The baseline value for efficacy and safety variables is the last available value collected prior to or at the first date of study treatment. Missing baseline data will not be imputed.

All data collected after the first date of treatment are defined as *post-baseline*. The *study day* for a baseline or post-baseline scheduled or unscheduled visit is defined as:

Study day = (Date of visit) – (Date of first dose of study treatment) + 1;

The study day for a scheduled or unscheduled visit before baseline is defined as

Study day = (Date of visit) – (Date of first dose of study treatment).

2.1.1.3 End of study/end of treatment/unscheduled visit day mapping:

The end of treatment date (date of last exposure from 'Study Treatment' CRF form) is the date of the last study treatment prior to/on the end of study date. The end of study date (from 'Study disposition' CRF) is the date when a subject completes or discontinues the study. For reporting data by visit in outputs, visit window (Section 2.1.1.5) rules will be applied based on study day to allocate assessments to the actual (reported) visit number.

2.1.1.4 Unscheduled visits

Unscheduled visit measurements will be included in the following:

- 1. derivations of measurements at scheduled visits per specified visit windowing rules below.
- 2. derivations of baseline/last on-treatment measurements.
- 3. derivations of the maximum/minimum on-treatment values and maximum/minimum changes from baseline values for safety analyses.
- 4. subject data listings where appropriate.

2.1.1.5 Visit Windows

Visit windows will be applied for all measurements except data from e-diary daily. Weekly mean will be calculated every 7 days starting from study day 1.

Novartis	For business use only	Page 11 of 33
SAP		CSAF312B12201

Allocation of accomments to enclusio visit window

Table 2-1 Allocation of assessments to analysis visit window				
Scheduled main visit name/label	Target study day	Analysis visit window in study days	Visit Label	
Visit 1 Screening	-84	≤ -1	Screening	
Visit 2 Baseline	1	1	Baseline	
Visit 3	14	2 - 21	Visit 3 (week 2)	
Visit 4	28	22 - 42	Visit 4 (week 4)	
Visit 5	56	43 - 70	Visit 5 (week 8)	
Visit 6 EOT	84	≥ 71	Visit 6 / EOT (week 12)	

To allocate assessments to each scheduled visit

Table 04

- If no measurement is available within a visit window, the assessment will be considered missing for the visit.
- If there is more than one measurement available within the same visit window, use the following rules:
 - 1. The record closest to the target day will be used.
 - 2. If there are multiple records with the same distance to the target day, the latest record will be used.
 - 3. If there are multiple records with the same distance on the same day, the average will be used.

2.1.1.6 7-day average of assessments

The Pain Severity Visual Analog Scale (VAS) score is captured in the e-diary daily by the patient for the entire 6 months of the study (observational period and treatment period), and weekly mean of the scores is calculated by averaging the available Pain Severity VAS scores during the 7 days of that week. Pain frequency will be analyzed in the same manner.

To calculate the frequency of artificial tear/gel/lubricant use, the information is captured daily as mentioned above, and the daily frequency collected by the patient in e-diary during the 7 days of that week will be averaged.

2.1.1.7 Change from baseline for continuous parameters

Change from baseline will be calculated as:

change from baseline = post-baseline value – baseline value

For summary statistics the raw values (and not imputed values) will be used.

2.2 Analysis sets

The Full Analysis Set (FAS) comprises all subjects to whom study treatment has been assigned by randomization. According to the intent to treat principle, subjects will be analyzed according

Novartis	For business use only	Page 12 of 33
SAP		CSAF312B12201

to the treatment and strata they have been assigned to during the randomization procedure. Misrandomized subjects who do not take study medication will be excluded from FAS.

The Safety Set (SAF) includes all subjects who received at least one dose of study treatment. Subjects will be analyzed according to the study treatment received, where treatment received is defined as the randomized treatment if the subject took at least one dose of that treatment or the first treatment received if the randomized treatment was never received.

The number and percentage of subjects within each of the above analysis sets will be summarized.

Rules of exclusion criteria of analysis sets with protocol deviations and subject classification are specified in Appendix.

2.2.1 Subgroup of interest

The subgroups of interest are specified below:

- Baseline age group: < 65 years, and >= 65 years
- Sex: male, female
- Race: Caucasian, Asian and Others
- Eye color:
 - 1. If the two irises of a subject are the same color as Black, Brown, Hazel, Green, Blue or Gray, the subject will be classified as one of the categories: "Black/Brown", "Hazel/Green", or "Blue/Gray".
 - 2. If the two irises of a subject are of the same color but different from the colors listed above, or if the two irises have a different color, the subject will be classified as "Other".
- Baseline pain severity: 7-day average pain severity VAS >= 75, 7-day average pain severity VAS < 75
- Region: Japan, Non-Japan

2.3 Subject disposition, demographics and other baseline characteristics

Subject characteristics and study conduct summaries include tables and listings such as subject disposition table, demographics and baseline characteristics tables, summary of screen failures by reason and listing of subjects excluded from analysis sets.

2.3.1 Subject disposition

Subject disposition will be summarized separately by treatment group and total for the FAS. Specifically, the number and proportion of subjects who discontinued the study will be summarized by treatment and total. The primary reason for premature study discontinuation will be summarized in the table.

Novartis	For business use only	Page 13 of 33
SAP		CSAF312B12201

2.3.2 Demographics and baseline characteristics

Demographics table will include age, sex, race, ethnicity, ancestry, and eye color.

Baseline characteristics table will include: type of prior surgery(PRK,LASIK, LASEK, RK, SMILE or Cataract), time (days) since last surgery, corneal fluorescein staining(sum score), conjunctival lissamine staining(sum score), conjunctival redness score (Temporal and Nasal), schirmer score, Pain Characterization Questionnaire (question 2 only), 7-day average of pain severity VAS score, 7-day average of pain frequency VAS score, 7-day average of artificial tear/gel/lubricant use frequency and 7-day frequency of rescue medication use .

Demographic and baseline characteristics will be summarized for FAS populations by treatment group using frequencies and percentages (for categorical variables) and descriptive statistics of mean, standard deviation, minimum, median and maximum (for continuous variables).

Relevant medical histories and current medical conditions at baseline will be summarized by system organ class, preferred term and treatment group, for ocular and non-ocular histories/conditions, respectively.

2.4 Treatments (study treatment, rescue medication, concomitant therapies, compliance)

The SAF will be used for the analyses below. Categorical data will be summarized as frequencies and percentages. For continuous data, mean, standard deviation, median, minimum, and maximum will be presented.

2.4.1 Study treatment / compliance

The duration of exposure in days to study treatment will be summarized by means of descriptive statistics by treatment group. The duration of exposure is defined as: date of the last administration of study treatment (date of last exposure in CRF 'Study Treatment' form) – date of first administration of study treatment (date of first exposure in CRF 'Study Treatment' form) + 4 + 1.

Compliance will be presented by summarizing the total number of days without missing a dose or dose interrupted within the treatment period by treatment group. Reason for premature discontinuation from the study treatment will also be summarized.

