6.1.3 Treatment arms/group

At Baseline (Visit 2), all eligible subjects will be randomized (ratio 1:1:1) via Interactive Response Technology (IRT) to one of the treatment arms in the double-blinded treatment.

- SAF312 Placebo eye drops, suspension, b.i.d.
- SAF312 5 mg/ml (0.5%) eye drops, suspension, b.i.d.
- SAF312 15 mg/ml (1.5%) eye drops, suspension, b.i.d.

`

Treatment duration

6.1.4

Subjects will dose both eyes with their assigned treatment for 12 weeks (84 days).

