12.3 Treatments

The Safety set will be used for the analyses below. Categorical data will be summarized as frequencies and percentages. For continuous data, mean, SD, median, 25th and 75th percentiles, minimum, and maximum will be presented.

The duration of exposure in days to SAF312 and placebo will be summarized by means of descriptive statistics using the safety set.

Concomitant medications and significant non-drug therapies prior to and after the start of the study treatment will be listed and summarized according to the Anatomical Therapeutic Chemical (ATC) classification system, by treatment group.

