12.5.1 Safety endpoints

For all safety analyses, the safety set will be used. The safety assessments are adverse events (ocular and non-ocular), slit lamp biomicroscopy, IOP, visual acuity, ophthalmoscopy, and corneal endothelial cells evaluations. All listings and tables will be presented by treatment group.

Safety summaries (tables, figures) include only data from the on-treatment period with the exception of baseline data which will also be summarized where appropriate (e.g. change from baseline summaries). In addition, a separate summary for death including on treatment and post treatment deaths will be provided. In particular, summary tables for adverse events (AEs) will summarize only on-treatment events, with a start date during the on-treatment period (treatment-emergent AEs).

The on-treatment period starts from the date of the first administration of study treatment to 4 days after the date of the last administration of study treatment.

The safety analysis will consist of descriptive summaries. Continuous variables will be presented with n, mean, SD, median, minimum and maximum. Categorical data will be displayed with frequency and percentage.

Adverse events

All information obtained on adverse events will be displayed by treatment group and subject.

The number (and percentage) of subjects with treatment emergent adverse events (events started after the first dose of study medication or events present prior to start of double-blind treatment but increased in severity based on preferred term) will be summarized in the following ways:

- by treatment, primary system organ class and preferred term.
- by treatment, primary system organ class, preferred term and maximum severity.
- by treatment, Standardized MedDRA Query (SMQ) and preferred term.

Ocular and non-ocular adverse events will be summarized separately. Separate summaries will be provided for study treatment related adverse events, death, SAE, other significant adverse events leading to discontinuation.

Subject listings of all adverse events will be provided. Deaths and other serious or clinically significant non-fatal adverse events will be listed separately. A subject with multiple adverse events within a primary system organ class is only counted once towards the total of the primary system organ class.

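### SAP 2.4.1 counts four drug-free follow-up days as exposure, so reported days of exposure are 4 too high in every arm

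*SAP*

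**What the plan says.** SAP 2.4.1 states that "The duration of exposure in days to study treatment will be summarized by means of descriptive statistics by treatment group". It defines that duration as the date of last administration minus "date of first administration of study treatment (date of first exposure in CRF 'Study Treatment' form) + 4 + 1", with both dates taken from the Study Treatment form of the CRF. It gives no reason for the 4.

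Four other places bear on the definition:

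- SAP 2.1.1.3 takes the date of last exposure from the same form as the end of treatment. It says that this date "is the date of the last study treatment prior to/on the end of study date".
- Protocol 6.1.4 fixes the planned course: "Subjects will dose both eyes with their assigned treatment for 12 weeks (84 days").
- Protocol 12.3 plans the same summary without any extension: "The duration of exposure in days to SAF312 and placebo will be summarized by means of descriptive statistics".
- Protocol 12.5.1 defines an on-treatment period for safety summaries, which runs from the first administration "to 4 days after the date of the last administration of study treatment".

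SAP 1.1 places the last treatment at Visit 6 and the end of study 4 days later. Protocol 9.3 describes that later contact as a telephone call about adverse events that began after the last dose. SAP Section 4 declares no change to the protocol-specified analyses.

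**The concern.** The formula carries two additions. The 1 is needed to count both the first and the last day. The 4 extends the count past the date that the SAP itself calls the end of treatment, into days on which no drops are planned. The result is the length of the safety on-treatment period, but the table will present it as days of exposure to study treatment.

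What is at stake is the absolute exposure figure in the study report. Protocol 4.2 gives the safety of prolonged TRPV1 inhibition as one reason for a 12-week treatment period, and a reader would take the exposure table as the record of how long subjects were on drug. Under this formula a full course appears longer than the protocol allows for, and a subject who stops a few days early can appear to have completed.

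**Working it through.** **Inputs**

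- First dose: Day 1. SAP 2.1.1.2: "Baseline (Day 1) is the date of first dose of study treatment".
- Planned dosing: 84 days (Protocol 6.1.4).
- Last dose: at Visit 6, target Day 84 with a window of ±2 days (SAP 1.1; Protocol Table 8-1).
- Inclusive counting: the SAP's own convention for study day. SAP 2.1.1.2: "Study day = (Date of visit) – (Date of first dose of study treatment) + 1".

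**Step 1. Reproduce the planned duration.** With the inclusive count, last − first + 1 = 84 − 1 + 1 = 84 days. This is the figure in Protocol 6.1.4, so the 1 alone is enough.

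**Step 2. Apply SAP 2.4.1 to the same dates.** Last − first + 4 + 1 = 84 − 1 + 4 + 1 = 88 days. The excess is 4 days, and 4/84 = 4.8%.

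**Step 3. Other last-dose days.**

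| Last dose | Inclusive days | SAP 2.4.1 | Excess |
|---|---|---|---|
| Day 1 | 1 | 5 | 4 (400%) |
| Day 14 | 14 | 18 | 4 (28.6%) |
| Day 28 | 28 | 32 | 4 (14.3%) |
| Day 56 | 56 | 60 | 4 (7.1%) |
| Day 82 | 82 | 86 | 4 (4.9%) |
| Day 84 | 84 | 88 | 4 (4.8%) |
| Day 86 | 86 | 90 | 4 (4.7%) |

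A subject whose last dose is on Day 80 reads as 80 − 1 + 4 + 1 = 84 days, the length of a full course.

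**Step 4. Effect on the planned statistics.** SAP 2.4 lists mean, SD, median, minimum and maximum. Protocol 12.3 adds the quartiles. Adding 4 to every subject's value raises each location statistic by 4 and leaves the SD unchanged. The same 4 is added in the placebo arm and in both SAF312 arms, so any difference between arms is also unchanged.

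**Step 5. Other uses of the number.** Adverse events are summarised as numbers and percentages of subjects (Protocol 12.5.1; SAP 2.8.1). Neither document plans an exposure-adjusted rate or a person-time denominator. The primary model in SAP 2.5.2 does not use exposure duration.

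**The case against.** The strongest reply is that the 4 is a convention and not a slip. A miscount would not keep the inclusive 1 and add a separate 4, and the 4 equals both the on-treatment extension in Protocol 12.5.1 and the interval from end of treatment to end of study. Protocol 12.3 gives no exposure formula for the SAP to contradict. Protocol 6.1.4 states planned dosing time and does not say what the summary variable must equal. The formula is printed in the SAP, so a reader can subtract 4.

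Part of this stands. The 4 probably was deliberate, and there is no clash between two written formulas. It does not rescue the label. The only 4-day extension of treatment time in the documents is a window for safety summaries, which is not time on drug. Nothing in SAP 2.4.1 or SAP Section 4 tells a reader of the table that drug-free days are included.

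The reply is right about consequences. A reader might infer that the inflated figures could distort the choice of concentration, dilute adverse event rates or mask poor tolerability in early stoppers. The documents do not support these readings:

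- The shift is identical in every arm, so it cannot favour one concentration. Neither document gives a dose-selection rule based on exposure duration.
- No planned rate uses exposure as its denominator.
- The effect of prolonged inhibition on the ocular surface is assessed through staining, Schirmer and redness scores at Week 12, not through days of exposure.
- The large percentages for very short courses are hypothetical cases, and no planned output shows relative exposure or exposure categories.
- SAP 2.4.1 separately summarises days without a missed or interrupted dose and the reasons for stopping treatment. Tolerability therefore does not rest on the exposure line alone.

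**Conclusion.** Wrong as written, and minor. The exposure summary will overstate time on study drug by exactly 4 days for every treated subject, and so will every mean, median, minimum and maximum. For a completer dosed on Days 1 to 84 the figure is 88 instead of 84. Across the visit window for the last dose it is 86 to 90 instead of 82 to 86. SDs, between-arm differences, adverse event percentages, efficacy results and the comparison of concentrations are unaffected.

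The conclusion rests on two assumptions: that the CRF date of last exposure is the actual date of the last dose, as SAP 2.1.1.3 says, and that no study drug is used after it. The 88-day figure also assumes a last dose exactly on Day 84. The 4-day excess does not depend on that.

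**What to change.** In SAP 2.4.1, define duration of exposure as date of last administration − date of first administration + 1. If the longer interval is wanted, report it as a separate line labelled *on-treatment period (last − first + 1 + 4 days)*, with a reference to Protocol 12.5.1.

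This costs one line of SAP text and one derived variable. No new data are needed, and no other planned analysis changes. The reported exposure figures become 4 days shorter in every arm.
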